**SIGNIFICANCE.** The current study proposes a scalable intervention designed to increase identification and linkage to CSC for adolescents involved in the JJS who present with psychosis spectrum symptomatology. Juvenile courts, and the JJS broadly, are increasing the proactive screening of youth for mental health symptoms. However, there is an inevitable lag between screening and an outpatient mental health appointment which, in turn, is followed by generally poor uptake of outpatient treatment. This application's approach is consistent with FOA language, specifically the NIMH interest in "better signal detection of psychosis onset, or symptoms suggesting high clinical risk of psychosis, within .... criminal justice agencies," as well as "methods to achieve expeditious referral of persons with first episode psychosis (FEP), or those at high clinical risk of psychosis, to an appropriate specialty care treatment program". As specified in the FOA, this planning grant application will also: "identify a baseline rate of DUP", as well as explore the occurrence of psychosis-spectrum symptoms among high risk JJ youth, "identify bottlenecks and gaps in the pathway to CSC care", and "develop and pilot test feasible strategies for substantially reducing DUP". The scientific premise of this research is supported by the need to develop more effective screening and linkage to service strategies during a youth's contact with the JJS, the virtual absence of such studies in the literature, and its enhancement by use of a conceptual model for implementation. Our study will provide data on screening delivered by JJS staff and improved linkage to follow-up mental health care as the clinical services mechanism hypothesized to reduce the DUI/DUP. As requested in the FOA, we will also "provide evidence of the association between those targets", i.e. latency to treatment linkage and engagement in treatment, and "the outcomes of interest (e.g., DIU/DUP, symptoms, and functioning)". In exploratory analyses, we will also assess potential moderators that may inform which youth most benefit from this screening/referral intervention, including adolescent sex, gender, race, ethnicity, and socioeconomic status, as well as service level factors, i.e., fidelity of JID and CSC staff to the referral process. This research also has the potential to directly inform clinical practices in JJS settings and has significant implications for scalability and dissemination. Scientific rigor is maintained by ensuring fidelity to the brief screening/referral protocol, study retention procedures, blinding of research assessors, data analytic strategies including missing data procedures, which are described in detail in the approach section below. Additionally, relevant biological variables, specifically sex, are considered in the

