
The assembled research team collectively brings expertise in the assessment of adolescents with a broad range of psychopathology, including psychosis-spectrum disorders, experience in conducting community-based research, and experience in improving assessment and referral within the juvenile justice system.

**Participants.** JJS offenders, ages 12- 17, will be eligible for enrollment with the following criteria: 1) legal guardian available to consent for juvenile’s participation, and adolescent assents to participate; 2) juvenile is English speaking; parents may be Spanish-speaking because we will have Spanish-speaking research staff and interpreter services available; and 3) juvenile flags positive on the MAYSI-2 Thought Disturbance subscale or the PQ-B. Exclusion criteria include: 1) observable developmental delays that would interfere with obtaining assent and/or accurate assessment, and 2) juvenile meets hospital level of care for imminent risk due to severity of symptoms, in which case they will be transported to Emergency Department per existing JID procedures. In addition, we will collect a comparison sample (n = 70) meeting these same inclusion/exclusion criteria with the exception that they will screen negative on the MAYSI- 2 Thought Disturbance subscale and PQ-B. This subgroup will be used in analyses exploring the sensitivity/specificity of the MAYSI-2 Thought Disturbance subscale and PQ-B.. The MAYSI-2 is a 52-item self-report measure for ages 12-17 that screens for current MH symptoms. The Thought Disturbance Subscale consists of 5 items, 4 of which refer to altered perceptions of reality and the fifth to de-realization. The developers do not recommend use of the subscale with girls. *The PQ-B, a 21 item measure for both males and females, with an 8th grade reading level and takes 3-4 minutes to complete. In a sample of 141 adolescents and young adults referred for assessment to prodromal research centers, the instrument achieved specificity of 0.68 and sensitivity of 0.88 with regard to SIPS diagnoses using a cutoff distress score threshold of six or greater on the weighted distress measure. A recent review indicated sensitivity ranging from .70-.97 across different samples*.

**Racial and ethnic minority considerations.** Consistent with 2016 RIFC statistics, ethnic representation will be approximately 18% Hispanic and racial representation will be about 22% African American or Black

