#### **Referral Conditions**

**Phase I, months 3 – 14: Standard Care (baseline control) condition.** In the Standard Care condition, if a teen has a positive screen on the MAYSI-2/PQ-B screening battery, JJS staff members determine whether there is need for further evaluation or concern of imminent risk. If there is concern for imminent risk, then the staff member contacts a clinician in the RIFC Mental Health Clinic for an emergency evaluation. If the teen is not at imminent risk, a referral to a community mental health clinic is arranged by the JJ intake worker. In this application, we will follow the same procedures, but if there is no imminent risk, the JID staff member will refer to the CSC rather than a community mental health clinic. *The CSC will evaluate the teen and offer services at the CSC if psychotic symptoms are a primary concern. CHR youth with other primary issues (e.g., trauma, substance use) are typically seen by other services in the mental health clinic which houses the CSC. All CHR youth who consent to the study will be seen for follow-up assessments and can be referred back to the CSC or mental health clinic to resume/initiate treatment if symptoms worsen. In the data analysis, we will record the percentage of youth referred to the CSC who are CHR/psychosis risk, as well as the services they receive and clinical outcome data at the 3 month follow-up assessment.* Data collected by Co-I [name] indicates that 26% of the youth that present to JID report that they are already receiving mental health treatment. In such cases, the families will be referred back to their mental health provider with the recommendation to consult the CSC.

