The main outcomes are individual and total symptom scores (reflecting intensity, interference, and conviction) as well as diagnosis (i.e., low-risk, high-risk, or psychosis) and illness trajectory (i.e. progression, persistence, and partial or full remission) from the SIPS. We will also examine treatment attendance, motivation for treatment, and treatment barrier reduction. The analysis framework will be linear regression, with psychosis-spectrum symptoms as the outcome and Enhanced Referral/Linkage to Care condition as the main predictor. In a randomized design, we would be certain that randomization introduced control for measured and unmeasured factors. In the baseline control design, we cannot be sure that secular trends might not cause different kinds of adolescents to become referred to JJ and/or influence their responses to questions about psychotic-like symptoms. For this reason, we will control for a select set of *a priori* identified confounding variables (sex, gender, race, ethnicity, and age), past history of psychosis-spectrum symptoms, and ongoing mental health treatment at the time of enrollment. The sign and standard error of the enhanced referral/linkage to care condition describes the magnitude and significance of the treatment effect at the threshold level of the screen. For the purposes of this pilot, key outcome parameters are the standard deviation of the SIPS positive symptom scores, the pre-post correlation of the SIPS scores, and the overall  $R^2$  in follow-up SIPS scores given pre-specified covariates. These parameters would be necessary to estimate the sample size requirements for a definitive trial.

**Aim 3C. Relationship between service mechanisms (treatment linkage and attendance) and psychotic symptoms/DUP.** Correlation and regression techniques will be used to examine how use of services over the 3-month study period is related to change in psychosis-spectrum symptoms as assessed by the SIPS as well as general symptomatology, as assessed by the BPM.

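### Aim 3C relates service use to symptom change without specifying adjustment for the baseline score, phase or any confounder, so a false link with improvement can arise if use follows baseline severity

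*Combined protocol and SAP*

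**What the plan says.** Aim 3C in the Data Analysis Plan is a single sentence. It will use correlation and regression to examine "how use of services over the 3-month study period is related to change in psychosis-spectrum symptoms". The outcomes are "change in psychosis-spectrum symptoms as assessed by the SIPS as well as general symptomatology, as assessed by the BPM". No model form, baseline term, phase term or covariate is given.

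The paragraph before it, for the Aim 3B phase comparison, lists covariates: sex, gender, race, ethnicity and age, together with "past history of psychosis-spectrum symptoms, and ongoing mental health treatment at the time of enrollment". Nothing carries that list over to Aim 3C, and the list does not include the baseline SIPS or BPM score.

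Other sections bear on who uses services:

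- Referral Conditions, Phase I: "The CSC will evaluate the teen and offer services at the CSC if psychotic symptoms are a primary concern". The same paragraph says that clinical high-risk youth in the study "can be referred back to the CSC or mental health clinic to resume/initiate treatment if symptoms worsen".
- Training in assessment: if parents ask, the research evaluation is passed to the CSC, in both phases.
- Participants: enrollment requires that the "juvenile flags positive on the MAYSI-2 Thought Disturbance subscale or the PQ-B".

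The Significance section promises evidence that links "latency to treatment linkage and engagement in treatment" to the outcomes of interest. Aim 3C is the analysis that relates service use to symptoms.

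**The concern.** A change score contains the baseline score with a negative sign. A youth whose baseline score is high partly by chance or because of a transient peak will tend to score lower at 3 months whatever care is received. If such youth also use more services, use and improvement become correlated without any effect of services.

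The documents make a link between severity and service use plausible. The CSC offers its services according to how prominent psychotic symptoms are, and research findings can reach the CSC. Families and clinicians choose service use, so it is at least as open to confounding as the phase comparison, for which the plan already accepts the need for covariates.

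At stake is the reading of the service mechanism: whether linkage and attendance appear to go with fewer symptoms. A team planning the larger study could take a built-in association for support.

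**Working it through.** **The plan's own figure.** Estimated sample size and retention rates gives 140 enrolled and 80% follow-up: 140 × 0.80 = 112, and 70 × 0.80 = 56 per phase. The plan states 110 in total (Power) and about 55 per phase, which agrees to within rounding. I use n = 110.

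**Inputs that the documents do not give (assumptions).**

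- r, the correlation of service use with the baseline score: 0.2 to 0.4.
- rho, the pre-post correlation of the symptom score: 0.4 to 0.7. The plan lists this as a quantity that the pilot will estimate.
- Two-sided alpha of 0.05. The plan states no test level for Aim 3C.
- Equal standard deviations at both visits and no true effect of services.

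**Case 1: service use (A) follows the observed baseline score (B).** Scale B and the follow-up score F to unit variance. Then corr(A, B) = r and corr(A, F) = r × rho. The covariance of A with F - B is -r(1 - rho), and the variance of F - B is 2(1 - rho). Hence

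corr(A, F - B) = -r × sqrt((1 - rho)/2).

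A negative value means that more services go with a larger fall in symptoms. The rejection rate comes from Fisher's z, with mean atanh(corr) × sqrt(107).

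| r | rho | Spurious correlation | Mean of z | False-positive rate |
|---|---|---|---|---|
| 0 | any | 0 | 0 | 5% |
| 0.2 | 0.7 | -0.077 | -0.80 | 12.6% |
| 0.3 | 0.5 | -0.150 | -1.56 | 34.6% |
| 0.4 | 0.4 | -0.219 | -2.30 | 63.4% |

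Simulation (4,000 runs per setting) agrees: at r = 0.3 and rho = 0.5 the unadjusted change score rejects in 36% of runs. Regression of F on A and B rejects in 5.4%. Over all settings tried in this case (r from 0 to 0.5, rho from 0.3 to 0.7) the adjusted model rejects in 4.2% to 5.9%.

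The first row also settles the role of screening. Enrolling youth for high screening scores can produce average improvement, but at r = 0 that improvement is unrelated to attendance.

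**Case 2: service use follows stable severity, not the error or transient part of the baseline score.** Now corr(A, B) = corr(A, F) = r, so the covariance of A with F - B is r - r = 0 and the change score is unbiased. The baseline-adjusted model is not. Its partial correlation is

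r(1 - rho) / sqrt((1 - r²)(1 - rho²)),

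with z mean atanh(partial correlation) × sqrt(106).

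| r | rho | Change score | Partial correlation, adjusted model | False-positive rate, adjusted model |
|---|---|---|---|---|
| 0.2 | 0.7 | 5% | +0.09 | 14% |
| 0.3 | 0.5 | 5% | +0.18 | 47% |
| 0.4 | 0.4 | 5% | +0.29 | 86% |

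The positive sign means that attenders appear to do worse. A single error-prone baseline score does not fully remove stable severity.

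**The case against.** The strongest reply has four parts.

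1. *The plan is silent and does not rule adjustment out.* Regression can include the baseline score. This stands: a reader might infer that the plan has chosen an unadjusted analysis, but the text does not say so. What can be said is that an unadjusted change-score correlation would comply with it.

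2. *Service use may not follow the research baseline score.* The CSC decides from its own evaluation and sees research results only at a parent's request. Screen-positive youth without imminent risk are referred whatever their severity, or sent back to their existing provider in Phase I if already in care. The CASA covers 31 settings, and the Background ties nonadherence to living situation, family functioning, disadvantage and motivation. This stands as a reason why r and its source are unknown. It does not show that r is zero.

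3. *Baseline adjustment can create an error of its own.* Case 2 confirms this. The documents do not settle which case applies, and a mixture is plausible. Adjustment therefore should not simply replace the change score.

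4. *Re-referral when symptoms worsen pushes the other way*, towards more services with worse outcomes. This stands. The net direction of bias cannot be read from the documents.

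A reader might also infer that enrollment on a high screen is enough to produce the false link. It is not, as the r = 0 row shows.

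**Conclusion.** The point holds as a conditional one. Aim 3C leaves the adjustment unspecified where service use plausibly depends on severity, and the simplest analysis that fits its wording can show a false benefit. Under Case 1 and the assumed ranges, the spurious correlation is about -0.08 to -0.22 and the false-positive rate about 13% to 63%. These are scenarios, not estimates for this trial: they need use to follow the observed baseline score, and they vanish at r = 0.

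The documents do not support the stronger reading that Aim 3C will necessarily favor services, or that baseline adjustment alone cures the problem. Aim 3C is a secondary analysis in a pilot. The Aim 2A linkage comparison is unaffected, as are the parameters that Aim 3B carries forward (SIPS standard deviation, pre-post correlation and R-squared). What is affected is the interpretation of the service mechanism, and the repair is cheap enough to make.

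**What to change.** Pre-specify for Aim 3C:

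1. Regression of the 3-month score (SIPS and BPM, each separately) on service use, adjusted for the baseline value of the same measure, study phase and all Aim 3B covariates: sex, gender, race, ethnicity, age, past history of psychosis-spectrum symptoms, and ongoing treatment at enrollment.
2. Beside it, the change-score model with the same phase term and Aim 3B covariates.
3. A rule that a link is stated only if the two models agree, and is described as an association. Neither model removes reverse causation (worsening that leads to more care) or unmeasured confounding.

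No new data are needed, because both phases complete the same assessments at baseline and 3 months. The cost is one extra model per outcome and a more cautious conclusion.

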**Fidelity to the Enhanced Referral/Linkage to Care condition.** We will have the CSC clinician, who will be employed by the research project but also work at the CSC, audiotape their conversation with the family in the enhanced referral phase of the study. The CSC clinician will use a hand-held audio recorder so that only the CSC clinician's portion of the conversation will be recorded. Fidelity will also be rated by interviewing the parent/caregiver at the baseline research assessment, which will typically occur within a week of the JID

appointment. Caregivers will be asked what the CSC intake worker said to them about scheduling a CSC appointment. The RA conducting the assessment will record verbatim the parent's responses. In both the clinician reported and parent reported data collection, fidelity will be rated by PI [name] and Co-Is [name] and [name] on a two-point scale (0= not satisfactory; 1= satisfactory). If there is disagreement, a consensus meeting will be held to resolve discrepancies in ratings.

**Baseline and follow-up assessment.** Families in both phases of the study will complete the same assessments at baseline and 3-month follow-up to gather data on treatment history, psychosis-spectrum symptoms, general psychiatric symptoms and functioning, as well as JJS contacts (see details below under Measures). In addition, at follow-up, we will interview families about barriers to treatment linkage and treatment satisfaction. The RA and Co-I [name] will be blind as to whether the families were seen for follow-up CSC or mental health care until after the interviews are completed.

We will also interview JID intake workers and CSC staff to assess both services and implementation factors related to referral process and completion. The baseline and follow-up assessment battery were designed to minimize participant burden and to thoroughly assess psychosis-spectrum symptoms. The follow-up assessment will be scheduled 3-months post-referral to the CSC. The 3-month follow-up period will allow us to assess whether high risk youth engage in treatment with the CSC or other mental

healthcare. Both baseline and follow up interviews will be conducted in-person and last approximately 1.5- 2 hours.

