**Aim 2B: Identify implementation and service level factors that promote/hinder linkage to the CSC.** Feasibility and Penetration, the number and percentage of JID personnel trained and consistency (% of time) using the enhanced referral protocol will be calculated with descriptive statistics. A rate of 80% will be the benchmark. Efficiency will be rated by the number of text message and phone contacts necessary to complete the referral to the CSC. A benchmark of two contacts will be considered an indicator of efficiency. Equity of enhanced referral protocol fidelity and treatment linkage across gender, race, and ethnicity will be compared across Phase I (Standard Care) and Phase II (Enhanced Referral/Linkage to Care condition), as well as cross-sectionally in the Enhanced Referral/Linkage to Care condition only, using cross-tabulation approaches. Acceptability. JJS staff perceived roles in screening and referral will be reported in percentages based on qualitative interviews as well as by mean, median, and range of scores on the Attitudes toward Mental Health

Screening measure. A total of 80% of the JID personnel scoring within one standard deviation of the mean on this measure based on the literature will be the benchmark.

**Aim 3A: Investigate client level factors at follow-up.** Attitudes about CSC referrals. These analyses follow the qualitative interview procedure described above. Rates of treatment initiation/retention in CSC services or other mental health care. Percentages of CSC participation will be calculated with 80% set as the benchmark as will other types of mental health care as rated on the CASA. For those already in mental health care at the time of enrollment, percentages of consultation to the CSC will be calculated, as will the types of treatment received and frequency/intensity of the services. Treatment barriers and motivation. Scores on the *Motivation for Youth's Treatment Scale* and the *Barriers to Treatment Participation Scale* will be analyzed using a paired t-test to determine any changes in these measures from baseline to three month follow-up. Treatment Satisfaction. These analyses follow the qualitative interview procedure described above.

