**Exploratory analyses.** In exploratory analyses, we will also assess potential moderators of the Enhanced Referral protocol effect. We are particularly interested in whether or not the effect of the Enhanced Referral protocol varies by sex, gender, race, ethnicity, and socioeconomic status, as well as service level factors, i.e., fidelity of JID and CSC staff to the referral process. These exploratory analyses will be accomplished by repeating our main analysis models, described above, but including main and interaction effects of selected potential moderators with study phase. Inference will be based on effect size statistics for interaction effects and used as hypothesis generating results for future studies.

**Power:** As mentioned above, per simulation studies conducted by Teare and colleagues (2014), a total sample size of 60 is sufficient to obtain reasonably precise estimates of key design parameters necessary to power a definitive trial with continuous outcomes. Therefore, our total sample of 140 at baseline and 110 at 3 month follow-up should be sufficient to conduct a simulation study and determine power for a definitive trial.

**Timeline: Months 1 - 2:** Start-up; **Months 3- 14:** 12 months of baseline data collection on Standard Care condition (baseline control); **Months 6 - 17:** 3 month follow-up on Standard Care condition; **Months 18 - 19:** Training of JID intake workers in Enhanced Referral/Linkage to Care protocol; **Months 20 - 31:** 12 months of data collection on the Enhanced Referral/Linkage to Care condition; **Months 23 – 34:** 3 month follow-up on Enhanced Referral/Linkage to Care protocol; **Months 35 - 36:** Analyze data and prepare manuscript.

**Future research.** As stated in the FOA, this R34 planning grant proposes “the developmental work to be performed that enhances the probability of success in a larger study” and “develops and refines the research strategies to be utilized in the subsequent large-scale study....as well as close gaps in the pathway to specialty

FEP care". If successful, this planning grant will set the stage for a Type III Effectiveness-Implementation design to test this implementation strategy while also collecting data on the Enhanced Referral protocol's effect on linkage to CSC level care, DUP, and psychosis-spectrum symptoms.

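### Fidelity to the enhanced protocol is defined only for Phase II, so its planned interaction with study phase and its cross-phase equity comparison cannot be estimated as written

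*Combined protocol and SAP*

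**What the plan says.** **Moderator models.** The exploratory analyses paragraph of the Data Analysis Plan lists sex, gender, race, ethnicity and socioeconomic status as moderators, "as well as service level factors, i.e., fidelity of JID and CSC staff to the referral process". All are handled in one way, by repeating the main models "including main and interaction effects of selected potential moderators with study phase". On interpretation it states: "Inference will be based on effect size statistics for interaction effects".

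**Equity.** Under Aim 2B, equity of "enhanced referral protocol fidelity and treatment linkage across gender, race, and ethnicity will be compared across Phase I (Standard Care) and Phase II", and the same sentence adds a second comparison, "as well as cross-sectionally in the Enhanced Referral/Linkage to Care condition only, using cross-tabulation approaches".

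**How fidelity is measured.** The section on fidelity to the Enhanced Referral/Linkage to Care condition gives two sources. In the first, the CSC clinician will "audiotape their conversation with the family in the enhanced referral phase of the study". In the second, caregivers are asked at the baseline assessment what the CSC intake worker told them about making an appointment. Both are rated 0 (not satisfactory) or 1 (satisfactory). The service-level measures section refers back to this rating and adds no Phase I version.

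**When the rated content exists.** The direct hand-off from the court intake worker to the CSC is described only for Phase II. Staff are trained in months 18-19, after Phase I recruitment (months 3-14) and follow-up (months 6-17).

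**The concern.** A moderator-by-phase interaction asks whether the phase difference changes with the level of the moderator. The moderator therefore has to vary in both phases. Fidelity to a protocol that had not been introduced, and in which nobody had been trained, has no natural Phase I value. The cross-phase equity table has the same difficulty, because one of its two sides is empty or constant.

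At stake is what the pilot can tell the next study about whether quality of delivery matters. The exploratory results are meant to generate hypotheses for that study. If the analysis is run as written, software will silently drop a column or drop all Phase I rows. What is left may then be reported as moderation of the phase effect when it is something else.

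**Working it through.** **Sample, checked against the plan.** The sample size section assumes about 100 positive screens per phase, 70% enrolment and 80% follow-up.

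- Enrolled per phase: 100 × 0.70 = 70.
- Followed to three months per phase: 70 × 0.80 = 56, or 112 in total.
- The plan states about 55 per phase and 110 in total, so its figures are reproduced to within rounding. The check uses 55 per phase.

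**Estimability.** Let P be phase (0 or 1) and F the 0/1 fidelity rating, which varies only in Phase II. The moderator model has columns [1, P, F, P×F].

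- If F = 0 throughout Phase I, then P×F = F in every row.
- If F = 1 throughout Phase I, then P×F = F + P − 1 in every row.
- If F is missing in Phase I, only Phase II rows remain, so P = 1 (the intercept) and P×F = F.

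| Phase I fidelity | Columns | Rank | Consequence |
|---|---|---|---|
| constant at 0 | 4 | 3 | interaction aliased |
| constant at 1 | 4 | 3 | interaction aliased |
| missing | 4 | 2 | phase and interaction both lost |
| comparison: sex, 29% female in both phases | 4 | 4 | estimable |

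The plan gives no expected fidelity rate, so the share rated satisfactory in Phase II was set in turn to 50%, 80% and 90%. The ranks were the same each time. Because these are identities between columns, neither a larger sample nor added covariates removes them. They apply equally to the logistic model for linkage and the linear model for symptoms.

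**What remains when Phase I is coded 0.** Dropping the redundant column leaves [1, P, F], with rank 3 and 110 − 3 = 107 residual degrees of freedom. In the linear model before covariates, the F coefficient is the satisfactory-minus-unsatisfactory difference within Phase II. The P coefficient is Phase II unsatisfactory minus Phase I. Neither is an interaction.

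**Precision of the Phase II-only contrast.** With n = 55 and a share q rated satisfactory, the standard error in outcome SD units is √[1/(55q) + 1/(55(1 − q))]. The difference detectable with 80% power at two-sided 0.05 is (1.960 + 0.842) × SE.

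| q (assumed) | Satisfactory / not | SE (SD) | Detectable difference (SD) |
|---|---|---|---|
| 50% | 27.5 / 27.5 | 0.27 | 0.76 |
| 80% | 44 / 11 | 0.34 | 0.94 |
| 90% | 49.5 / 5.5 | 0.45 | 1.26 |

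**The case against.** **Phase I ratings are not expressly ruled out.** Only the audiotape is explicitly confined to the enhanced phase. The caregiver question carries no stated phase limit, families in both phases complete the same assessments, and the moderator is worded as "fidelity of JID and CSC staff to the referral process" rather than fidelity to the enhanced protocol. Phase I also has a defined referral step from court intake to the CSC. This stands to the extent that the absence of Phase I values is an inference. It is a strong one. The caregiver question sits under the heading on fidelity to the Enhanced condition, and the listed content of the common battery does not include fidelity. The court staff checklists are described with the enhanced training and never defined as a fidelity score. If some Phase I caregivers did give varying answers, the matrix could reach full rank. The score would then describe something other than delivery of the enhanced protocol, and would probably rest on few cases.

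**A usable contrast survives.** This also stands. With Phase I coded 0, the software leaves the Phase II contrast. A reader might infer that this coding turns the whole phase effect into a fidelity effect, or leaves no residual degrees of freedom. Neither follows: phase stays in the model with its own coefficient, and 107 residual degrees of freedom remain. The fault is aliasing.

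**Aim 2B already has a Phase II-only comparison.** Correct. Its sentence joins two measures with two comparisons and may simply be loosely drafted. Only one pairing, fidelity across phases, is impossible.

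**The analyses are exploratory.** True, and this limits the consequences. It does not make an unidentified coefficient computable.

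**Conclusion.** Two stated analyses cannot be run as written: the fidelity-by-phase interaction and the cross-phase comparison of fidelity equity. The interaction is aliased if Phase I fidelity is constant, and phase itself is lost if it is missing. The effect size that the plan would interpret is therefore undefined for this moderator. The conclusion rests on reading the fidelity rating as applying to the Enhanced condition, which its heading, its content and the training dates all support.

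The reach is limited. A reader might infer that the trial's main comparison is compromised or that fidelity cannot be studied at all. The documents support neither. The Aim 2A comparison of linkage, the Aim 3B variance and correlation parameters that are the pilot's stated purpose, the five demographic and socioeconomic moderators, and the Phase II-only equity comparison are all untouched. This should be corrected before analysis, but it does not threaten the pilot's main outputs.

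**What to change.** 1. Remove fidelity from the list of moderators tested by interaction with study phase. Leave the other moderators as they are.
2. Estimate the association of fidelity with linkage (about 70 enrolled) and with three-month outcomes (about 55) within Phase II only. Adjust for the a priori covariates where numbers allow: at 90% satisfactory, only 70 × 0.10 = 7 enrolled youth, or 5 to 6 at follow-up, would be in the smaller group.
3. Label the result an observational association within Phase II, not moderation of the phase effect.
4. In Aim 2B, limit the cross-phase equity comparison to linkage, and keep the already planned Phase II-only comparison for fidelity.

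The cost is a change of wording, with no new data. The downside is imprecision: over the assumed range of ratings, only differences of about 0.76 to 1.26 SD would be detectable with 80% power. The result should therefore be reported as an estimate with its interval, and the absence of a clear difference should not be read as evidence that fidelity is unimportant.
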